### **10.1.3 Collection of Specimens**

Blood samples will be collected on Day 1. For patients who undergo resection, samples will also be collected between one and three months after surgery to account for half-life of metabolites and determine if tumor burden influences metabolite levels. Approximately 30 ml blood will be collected into three red top tubes from each patient via venipuncture or port.

### **10.1.4 Handling of Specimens**

Samples will be left at room temperature for two hours to coagulate. Samples will then be centrifuged at 1000 g for 15-20 minutes and serum collected.

All specimens will be handled according to universal precautions. They will be stored in the [name] lab. Samples will be labeled with the patient's study number and will not contain any patient identifiers.

### **10.1.6 Methods**

- ELISA kits should be brought to room temperature prior to assays (at least 30 minutes)
- All samples will be run fresh
- ELISAs will be carried out according to kit protocol. All necessary reagents are provided within kits.
  - Kynurenone ELISA - Biovision (E4629-100)
  - Melatonin ELISA - Biovision (E4630-100)
  - Serotonin ELISA - Biovision (E4294-100)

(ELISA kits are suited for either plasma or serum).

- Standards should be run in triplicate
- Optimal dilution factor should be determined for human subjects (1:10 for mice)
- Samples are analyzed using a microplate reader, absorbance (450 nm)

## 10.2 Tissue Specimen Assays

### 10.2.1 Background

The serotonin theory of depression is supported through clinical experience. Selective serotonin reuptake inhibitors (SSRIs) remain the most common class of medicines used to treat depression. Mechanistically, these drugs increase serotonin levels at brain synapsis . Tryptophan is the principal substrate for serotonin synthesis, and therefore, tryptophan breakdown may have biologic implications on clinical depression in patients with dysregulated tryptophan catabolism. We and others have demonstrated that the enzymes responsible for tryptophan metabolism are dysregulated in pancreatic cancer . Specifically, the enzymes that divert tryptophan into kynurenine and related metabolites are overexpressed, including IDO1, IDO2, and TDO. This pathway effectively shunts tryptophan away from serotonin synthesis.

### 10.2.2 Rationale

In this study, we will examine the expression of each of these tryptophan degrading enzymes in resected PDAs (25 of 46 patients in the trial are expected to have resected specimens for analysis). We will determine if a correlation exists between expression levels of these enzymes in the tumor and 1) depression at baseline, and 2) the development of depression in patients on trial.

### 10.2.3 Collection of Specimens

Patients undergoing resection after completion of the study will have tumors collected and assayed for IDO1, IDO2, and TDO2 expression. This will be performed on sections prepared from resected specimens. Blocks will be requested from pathology and pulled for each patient and immunohistochemical staining will be performed.

### 10.2.4 Handling of Specimens

All specimens will be handled according to universal precautions. They will be stored in paraffin embedded blocks in the [name] lab. Samples will be labeled with the patient's study number and will not contain any patient identifiers. Samples will be stored for up to two years.

### 10.2.6 Methods

Collected tumors will be assayed for IDO1, IDO2 and TDO2 expression. We will test to see if expression of these enzymes correlate with depression scores or response to treatment.

## 11.0 STUDY PARAMETERS AND CALENDAR

### 11.1 Study Parameters

#### 11.1.1 Screening Evaluation:

The following must be completed within 28 days of initiating treatment:

- Informed consent
- Medical history
- Review of current medications
- Physical exam to include head and neck, pulmonary, cardiovascular, gastrointestinal, musculoskeletal, cognitive and cutaneous systems
- Electrocardiogram
- Pregnancy test for patients of child-bearing potential (ie. women who are pre-menopausal or not surgically sterile)
- ECOG

The following must be completed Week 1, Day 1 (clinic visit):

- ECOG performance status
- Blood collection for plasma metabolites
- FIBSER Side effect questionnaire
- QIDS-SR baseline survey for depression
- PHQ-9 Patient Health Questionnaire
- FACT-Hep quality of life survey
- Provide supply of blinded escitalopram/placebo and pill diary to patient
- Explain study procedures including dosing, completion of pill diary and questionnaires
- Toxicity assessment

#### 11.1.2 Treatment Period (these visits have window of +/- 7 days)

Daily:

- Escitalopram (Lexapro) is an SSRI (1 capsule) 10mg/ day for 2 weeks followed by Escitalopram (Lexapro) is an SSRI (2 capsules) 20mg/ day for 8 weeks followed by Escitalopram (Lexapro) is an SSRI (1 capsule) 10mg/ day for 2 weeks
- Patients randomized to the placebo arm will receive the same dose schedule but no active drug.
- Pill diary.

Every 2 weeks (phone call or clinic visit):

- QIDS-SR
- PHQ-9
- FIBSER
- Toxicity assessment
- Review drug diary compliance

Weeks 3 and 11 (clinic visit)

- Turn in unused pills and pick up new supply

- Review pill diary and pick up new diary

Once per month (phone call or clinic visit):

- FACT-Hep

Week 13 (end of treatment clinic visit):

- Collect pill diary
- Medical History
- Physical exam
- ECOG Performance Status
- QIDS-SR (via phone or mail)
- PHQ-9
- FIBSER (via phone or mail)
- FACT-Hep
- Toxicity Assessment

Week 25 (phone call or clinic visit)

- QIDS-SR (via phone or mail)
- PHQ-9
- FIBSER (via phone or mail)
- FACT-Hep
- Toxicity Assessment

Follow-up (every 12 weeks, via EMR review, patient visit or phone call)

- Assessment of disease and survival status, treatment details
- Tissue will be obtained from patients who undergo resection and stored in paraffin embedded blocks
- Patients who undergo tumor resection will have blood samples drawn for plasma metabolites 1-3 month after surgery

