### **6.3 Duration of Follow-Up**

#### **End of Treatment Study Procedures**

An end of treatment visit will be conducted on Day 85 (Week 13). This will be a clinic visit and will include a physical exam, collection of pill diary and any unused pills, toxicity assessment, QIDS-SR, PHQ-9, Fact-Hep and FIBSER. The patient's disease and treatment status will also be assessed.

During Week 25 (12 weeks after the end of treatment), a phone visit will be conducted which will include a toxicity assessment, QIDS-SR, PHQ-9, Fact-Hep and FIBSER. Patients who screen above 11 on the QIDS-SR or above 9 on the PHQ-9 will be referred by the study team to a social worker, who will then conduct their own assessment and make appropriate referrals to psychiatry if necessary. Patients who give an affirmative reply to Question 12 on the QIDS-SR or 9 on the PHQ-9 indicating thoughts of suicide, will be referred to Seidman Psychiatry Service for evaluation (please see Section 7.0).

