## 11.1.2 Study Calendar

Assessments	Screening (within 28 days before treatment)	D1	D8  Wk2	D15 Wk 3 (increase to 20mg)	D22  Wk4	D36  Wk6	D50  Wk8	D64  Wk 10	D71 Wk11 (decrease to 10mg)	D78  Wk12	D85  Wk13 (end of treatment)	Wk 25	Follow- up: every 3 mos x 3 years 	1-3 mos after surgery (if applicable)
Informed consent	✓													
Medical history /physical 	✓										✓			
ECOG performance status	✓	✓									✓			
ECG	✓													
Pregnancy test	✓													
Study visits*		✓ clinic	✓ phone	✓ clinic	✓ phone	✓ phone	✓ phone	✓ phone	✓ clinic	✓ phone	✓ clinic	✓ phone		
Serum metabolites 		✓												✓ 
Treatment escitalopram vs. placebo (10mg or 20mg) per day 		✓	✓	✓	✓	✓	✓	✓	✓	✓				
Pill diary 		✓	✓	✓	✓	✓	✓	✓	✓	✓	✓			
Toxicity assessment		✓	✓ 		✓ 	✓ 	✓ 	✓ 		✓ 	✓	✓ 		
QIDS-SR (Depression)		✓	✓ 		✓ 	✓ 	✓ 	✓ 		✓ 	✓	✓ 		
PHQ-9 Health Questionnaire		✓	✓ 		✓ 	✓ 	✓ 	✓ 		✓ 	✓	✓ 		
FACT-Hep (Quality of Life)		✓			✓ 		✓ 			✓ 	✓	✓ 		

FIBSER side effect questionnaire)		✓	✓ 		✓ 	✓ 	✓ 	✓ 		✓ 	✓	✓ 		
Tissue obtained if resection done													✓	
Disease/survival status/treatment details											✓	✓	✓	

History must include a review of current medications. Physical must include head and neck, pulmonary, cardiovascular, gastrointestinal, musculoskeletal, cognitive and cutaneous systems

Collect 30ml in three 10ml red top tubes prior to dosing.

Blinded escitalopram vs placebo is to be taken daily days 1 through 84 (10mg wks 1-2., 20mg wks 3-10, 10mg wks 11-12) unless dose reduction/drug discontinuation is required.

Diary is to be completed daily by patients and reviewed with clinical study staff during study visits to confirm compliance. Patients are required to come to the clinic on Days 15 and 71 to pick up drug supply and new pill diary. Unused pills and final pill diary will be returned at the end of treatment visit (Day 85).

 +/- 7 days

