### **Treatment failures**

Patients with high risk for suicide, suicide attempts, or a score of  $\geq 16$  points on the QIDS-SR at 12 weeks will be considered “treatment failures” and will be provided referrals for more optimal depression treatment throughout the duration of the study. Patient scores and adverse events will be reviewed by clinical study staff (RN or MD) within 24 hours of collecting information from patients to determine if additional action is needed per Section 7. Cases of suspected suicidal ideation will be reviewed within four hours as noted in Section 7, and study staff will immediately take action as appropriate upon review.

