#### CHECK THE ONE RESPONSE TO EACH ITEM THAT BEST DESCRIBES YOU FOR THE PAST SEVEN DAYS.

##### During the past seven days...

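### The end-of-treatment QIDS-SR may be completed as late as Day 92, and by mail, although dosing ends on Day 84, so some forms can recall days off study drug

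*Combined protocol and SAP*

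**What the plan says.** **Window.** The heading of Section 11.1.2, whose list includes Week 13, reads "Treatment Period (these visits have window of +/- 7 days". In the Study Calendar the Day 85 (Week 13) column carries footnote 5, which is the same 7-day allowance on either side.

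**Dosing.** Calendar footnote 3 states: "Blinded escitalopram vs placebo is to be taken daily days 1 through 84".

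**Recall.** The QIDS-SR form in Appendix IV instructs: "CHECK THE ONE RESPONSE TO EACH ITEM THAT BEST DESCRIBES YOU FOR THE PAST SEVEN DAYS".

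**Mode.** Section 6.3 says of the Day 85 visit: "This will be a clinic visit and will include a physical exam, collection of pill diary and any unused pills, toxicity assessment, QIDS-SR". The calendar also marks Day 85 as a clinic visit, and the Week 13 list in Section 11.1.2 is itself headed as one. Yet that list has the entry "QIDS-SR (via phone or mail", with no date by which a mailed form must be completed or returned.

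**Unblinding.** Section 6.1 (Unblinding Procedures) has patients unblinded at the Day 85 visit and lets those who received escitalopram continue on commercial supply. It does not say that the questionnaires come first.

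**Primary time point.** Section 14.2 sets the primary endpoint at 12 weeks without giving a study day. The calendar labels Day 78 as Week 12 and Day 85 as Week 13. Section 3.4 counts survey time from the first day of medication as day zero.

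**The concern.** The Day 85 assessment is meant to describe patients at the end of a 12-week course. A window that extends a week past the last dose lets some forms describe a mixture of treated and untreated days. Only the active arm has drug to lose, so any fading of effect after the last dose would raise scores in that arm and shrink the difference between arms.

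The mail route adds two problems. The completion date is uncontrolled, so a form can be filled in beyond the window or after the patient has learned the assignment, which matters for a self-reported outcome. The answer to item 12, on thoughts of death or suicide, also stays unseen until the form arrives, whereas Section 14.2 says: "Cases of suspected suicidal ideation will be reviewed within four hours as noted in Section 7".

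**Working it through.** **1. Last dosing day.** Section 6.1 gives 2 + 8 + 2 weeks. (2 + 8 + 2) × 7 = 84 days, so a course that starts on Day 1 ends on Day 84. This reproduces calendar footnote 3.

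**2. Allowed completion days.** 85 − 7 = 78 and 85 + 7 = 92, which gives Days 78 to 92, or 15 days.

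**3. Recall days after the last dose.** For completion on Day v:
- completion day not counted (recall is v − 7 to v − 1): off-drug days = max(0, v − 85)
- completion day counted (recall is v − 6 to v): off-drug days = max(0, v − 84), at most 7

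| Completion day | Not counted | Counted |
|---|---|---|
| 84 or earlier | 0 of 7 | 0 of 7 |
| 85 | 0 | 1 |
| 86 | 1 | 2 |
| 88 | 3 | 4 |
| 90 | 5 | 6 |
| 91 | 6 | 7 |
| 92 | 7 | 7 |

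Under the first count, 7 of the 15 allowed days (Days 86 to 92) include at least one off-drug day. This is a share of calendar days, not a forecast of how many patients are seen on them.

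**4. The same check for Day 78.** Its window is Days 71 to 85 (78 − 7 to 78 + 7). The latest completion, on Day 85, has 0 off-drug recall days, or 1 if the completion day is counted. The two windows overlap on Days 78 to 85.

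**5. Which visit is the 12-week assessment?**
- *For Day 78:* the calendar labels it Week 12. The model in Section 14.2 has 6 post-randomization measurements, which matches Days 8, 22, 36, 50, 64 and 78. Day 85 would be a seventh.
- *For Day 85:* with the first dose as day zero (Section 3.4), calendar Day 85 is 85 − 1 = 84 days later, and 84 / 7 = 12 weeks. Day 78 is 77 / 7 = 11 weeks. The objective in the Protocol Summary is the effect of 12 weeks of treatment, and only Day 85 follows a full course.

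The documents do not settle this.

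**6. Size of bias.** The documents give no figure for residual effect or symptoms after the last dose, and no distribution of visit dates. No bias can be calculated. The power statement in Section 14.3 does not depend on visit timing and is not in question here.

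**The case against.** The strongest reply is that Day 78 may well be the primary assessment. By step 4 the problem then hardly reaches the primary comparison. This stands, and it limits the point. A reader might infer that the primary result is biased toward no effect; the plan does not establish that Day 85 is primary, so the inference is not supported.

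Second, wholly off-drug recall needs completion on Day 92, or on Day 91 with the completion day counted. At the nominal Day 85 the recall is all or nearly all on drug. This also stands: the extreme case is an edge of the window, or a late mailed form, not the typical patient.

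Third, a reader might infer that a null result could not be told apart from an effect lost in the step-down weeks. The documents do not support that. At nominal timing the recall weeks for Days 36, 50 and 64 (Days 29–35, 43–49 and 57–63) lie wholly within the 20 mg period, Days 15 to 70. The time-by-arm interaction in Section 14.2 gives a relative risk at each visit, so Day 64 can be set against Days 78 and 85, though with limited precision. The step-down is also part of the intervention as defined, so measuring at its end is not a defect in itself.

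Fourth, a reader might infer that the mail option defeats the screening for suicidal ideation. It does not go that far. The Week 13 list gives no mail route for the PHQ-9, whose item 9 also asks about ideation, and the visit remains a clinic visit. What is left is a delay in seeing item 12 and a contradiction between sections.

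None of these replies explains why the window should run past the last dose, or reconciles the mail option with the clinic visit.

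**Conclusion.** The point holds as a flaw in timing and consistency at the end-of-treatment assessment. In-window forms can carry up to 7 of 7 recall days after the last study dose, and a mailed form can be later still and unblinded. The day counts assume that dosing ends on Day 84 as scheduled. Off drug here means after the last scheduled study dose; it implies nothing about residual effect.

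If Day 85 is the 12-week assessment, the flaw reaches the primary endpoint, and loss of effect would act toward no difference. That direction is an inference; the documents do not allow its size to be stated. If Day 78 is the assessment, the flaw is essentially confined to the Day 85 visit. Either way this is a cheap improvement worth making, not a fault that undermines the design.

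**What to change.** - Name the visit and study day that supply the 12-week primary assessment. If it is Day 85, bring the count of repeated measurements in Section 14.2 into line (six through Day 78, seven with Day 85).
- Close the end-of-treatment window for the QIDS-SR and PHQ-9 no later than Day 85. If the clinic visit runs late, complete both by live phone call inside the window.
- Set the Day 78 and Day 85 questionnaire windows so that they do not overlap. At present both allow Days 78 to 85, so one day could serve for both.
- Require both questionnaires to be completed before the patient is unblinded.
- Delete the mail option for the Week 13 QIDS-SR, so that Section 11.1.2 agrees with Section 6.3 and the calendar.

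The cost is a short amendment to Section 11.1.2, the calendar and its footnote 5, Section 6.1 and Section 14.2, with an occasional extra phone call and a tighter window for staff. No change to dosing is proposed, and no assessment is added.

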## 11.1.2 Study Calendar

Assessments	Screening (within 28 days before treatment)	D1	D8  Wk2	D15 Wk 3 (increase to 20mg)	D22  Wk4	D36  Wk6	D50  Wk8	D64  Wk 10	D71 Wk11 (decrease to 10mg)	D78  Wk12	D85  Wk13 (end of treatment)	Wk 25	Follow- up: every 3 mos x 3 years 	1-3 mos after surgery (if applicable)
Informed consent	✓													
Medical history /physical 	✓										✓			
ECOG performance status	✓	✓									✓			
ECG	✓													
Pregnancy test	✓													
Study visits*		✓ clinic	✓ phone	✓ clinic	✓ phone	✓ phone	✓ phone	✓ phone	✓ clinic	✓ phone	✓ clinic	✓ phone		
Serum metabolites 		✓												✓ 
Treatment escitalopram vs. placebo (10mg or 20mg) per day 		✓	✓	✓	✓	✓	✓	✓	✓	✓				
Pill diary 		✓	✓	✓	✓	✓	✓	✓	✓	✓	✓			
Toxicity assessment		✓	✓ 		✓ 	✓ 	✓ 	✓ 		✓ 	✓	✓ 		
QIDS-SR (Depression)		✓	✓ 		✓ 	✓ 	✓ 	✓ 		✓ 	✓	✓ 		
PHQ-9 Health Questionnaire		✓	✓ 		✓ 	✓ 	✓ 	✓ 		✓ 	✓	✓ 		
FACT-Hep (Quality of Life)		✓			✓ 		✓ 			✓ 	✓	✓ 		

FIBSER side effect questionnaire)		✓	✓ 		✓ 	✓ 	✓ 	✓ 		✓ 	✓	✓ 		
Tissue obtained if resection done													✓	
Disease/survival status/treatment details											✓	✓	✓	

History must include a review of current medications. Physical must include head and neck, pulmonary, cardiovascular, gastrointestinal, musculoskeletal, cognitive and cutaneous systems

Collect 30ml in three 10ml red top tubes prior to dosing.

Blinded escitalopram vs placebo is to be taken daily days 1 through 84 (10mg wks 1-2., 20mg wks 3-10, 10mg wks 11-12) unless dose reduction/drug discontinuation is required.

Diary is to be completed daily by patients and reviewed with clinical study staff during study visits to confirm compliance. Patients are required to come to the clinic on Days 15 and 71 to pick up drug supply and new pill diary. Unused pills and final pill diary will be returned at the end of treatment visit (Day 85).

 +/- 7 days

QoL assessments and Toxicity assessment will be completed with clinical study staff over the phone or in person if the patient's regular chemotherapy visit coincides with a study visit.

Patients will continue to be followed for survival for three years or until deceased (whichever occurs first).

Patients who undergo tumor resection will have repeat correlative plasma samples collected one to three months after surgery.

## **12.0 MEASUREMENT OF EFFECT**

Efficacy will be defined as the prevention of incidents of moderate or greater depression defined as a QIDS-SR score greater than 11 at 12 weeks.

## **13.0 DATA REPORTING / REGULATORY CONSIDERATIONS**

Adverse event lists, guidelines, and instructions for AE reporting can be found in Section 8.0 (Adverse Events: List and Reporting Requirements).

### **13.1 Data Reporting**

The OnCore™ and Forte EDC Databases will be utilized, as required by the Case Comprehensive Cancer Center, to provide data collection for accrual entry. OnCore™ is a Clinical Trials Management System housed on secure servers maintained at Case Western Reserve University. OnCore™ has the capability to facilitate study setup, activation, tracking, reporting, data monitoring and review, and eligibility verification.

The investigators are responsible for ensuring the accuracy, completeness, legibility, and timeliness of the data reported. All source documents must be completed in a neat, legible manner to ensure accurate interpretation of data. The investigators will maintain adequate case histories of study participants, including accurate case report forms (CRFs), and source documentation.

### **Data Management Responsibilities**

Data collection and accurate documentation are the responsibility of the study staff under the supervision of the investigator. All source documents and laboratory reports must be reviewed by the study team and data entry staff, who will ensure that they are accurate and complete. Unanticipated problems and adverse events must be reviewed by the investigator or designee.

### **Data Capture Methods**

The University Hospitals Research Information System (REDCap) database will be used for this study to record clinical data and toxicity-related data.

### **Types of Data**

Data will be maintained on paper source documents and entered into REDCap for data analysis. Captured data include patient medical history, laboratory values, treatment data and compliance, toxicity data, survival and outcome data, survey data, and radiographic data.

### **Study Records Retention**

Data will be maintained for at least two years after closure of the study and final data analysis.

## **13.2 Regulatory Considerations**

The study will be conducted in compliance with ICH guidelines and with all applicable federal (including 21 CFR parts 56 & 50), state or local laws.

### **13.2.1 Written Informed consent**

Provision of written informed consent must be obtained prior to any study-related procedures. The Principal Investigator will ensure that the subject is given full and adequate oral and written information about the nature, purpose, possible risks and benefits of the study as well as the

subject's financial responsibility. Subjects must also be notified that they are free to discontinue from the study at any time. The subject should be given the opportunity to ask questions and be allowed time to consider the information provided.

The original, signed written Informed Consent Form must be kept with the Research Chart in conformance with the institution's standard operating procedures. A copy of the signed written Informed Consent Form must be given to the subject. Additionally, documentation of the consenting process should be located in the research chart.

### **13.2.2 Subject Data Protection**

The study subjects will be assigned a unique study identification number that will be used on all study data forms, and other study records. Patient names, initials and/or hospital IDs will not be used as protocol identifiers. Randomization records will be maintained by the Seidman Cancer Center, Clinical Trials Unit Quality Assurance Team at a secure location at [name].

In accordance with the Health Information Portability and Accountability Act (HIPAA), a subject must sign an authorization to release medical information to the sponsor and/or allow the sponsor, a regulatory authority, or Institutional Review Board access to subject's medical information that includes all hospital records relevant to the study, including subjects' medical history.

